6.2 Bomedemstat Dose Titration to Platelet Count

Bomedemstat dose titration to platelet count will be performed according to the titration and re-challenge rules described in Table 6.1 and Table 6.2 as follows. Dose titration rules use the absolute platelet count and the relative change from the most recent scheduled assessment. Prior to cycle 2 day 1, dose increases are not permitted, and dose titration should be performed according to Table 6.1. Starting on Day 1 of cycle 2, dose increases are permitted, and dose titration should be performed according to Table 6.2. The maximum allowed dose is 6 mg/kg/d. Dose increases require adequate neutrophil and erythrocyte indices, and dose increases are not permitted within 21 days of a previous dose change, where change is inclusive of dose increase or dose reduction. After a dose hold, when platelets have returned to $>50 \times 10^3/\text{mCL}$, the subject should be re-challenged with bomedemstat at 50% of the previous dose. Dose reductions for safety reasons are permitted at any time.

Table 6.1. Bomedemstat titration to goal platelet count and re-challenge rules for cycle 1, days 8 and 15.

Platelet Assessment		Rules		
Platelet count ($\times 10^3/\text{mCL}$)	Change in Platelet Count Relative to Previous Scheduled Assessment	Titrate Dose?	Titration Rule	Re-challenge Rule
≥ 100	Any, including same count	Maintain	N/A	N/A
50-99	Any increase or same count	Maintain	N/A	N/A

50-99	<50% decrease ¹	Down-titrate ¹	Decrease current dose by 0.1 mg/kg¹	N/A
50-99	≥50% decrease ¹	Down-titrate ¹	Decrease current dose by 0.2 mg/kg if starting dose was 0.5 mg/kg or by 0.1 mg/kg if starting dose was 0.4 mg/kg¹	N/A
<50	Any change ¹	HOLD DOSE¹	HOLD DOSE¹	Resume at 50% of previous dose when platelets return to $>50 \times 10^3/\text{mCL}$. ²

1. If pseudothrombocytopenia due to blood sample coagulation or platelet clumping is suspected, the CBC should be repeated. If the second blood draw confirms that the first draw yielded a falsely low platelet count, the result of the first draw should be ignored and the dose of bomedemstat calculated based on the result of the second draw.
2. ANC $\geq 1.0 \times 10^3/\text{mCL}$ ($1.0 \times 10^9/\text{L}$) and Hgb $\geq 8 \text{ g/dL}$ (80 g/L) are needed for or re-challenge.

Table 6.2. Bomedemstat titration to goal platelet count and re-challenge rules for all days with CBC evaluation in cycle 2 and beyond.

Platelet Assessment		Rules		
Platelet count (x 10 ³ /mCL)	Change in Platelet Count Relative to Previous Scheduled Assessment	Titrate Dose?	Titration Rule	Re-challenge Rule
≥200	Any, including same count	Up-titrate ^{1,2,3}	Increase current dose by 0.15 mg/kg	N/A
100-199	<75% decrease ⁴ or same count or any increase	Up-titrate ^{1,2,3}	Increase current dose by 0.1 mg/kg	N/A
100-199	≥75% decrease ⁴	Maintain ⁴	N/A	N/A
50-99	<50% decrease ⁴ or same count or any increase	Maintain ⁴	N/A	N/A
50-99	≥50% decrease ⁴	Down-titrate ⁴	Decrease current dose by 0.1 mg/kg or 25% , whichever results in a lower dose	N/A
<50	Any change ⁴	HOLD DOSE⁴	HOLD DOSE⁵	Resume at 50% of previous dose when platelets return to > 50x10 ³ /mCL. ¹

1. ANC ≥ 1.0 x 10³/mCL (1.0 x 10⁹/L) and Hgb ≥ 8 g/dL (80 g/L) are needed for up-titration or re-challenge.
2. Dose up-titration is not permitted if any dose change (including up- or down-titration) has occurred within the previous 21 days.
3. The maximum allowed dose of bomedemstat is 6 mg/kg/d.
4. If pseudothrombocytopenia due to blood sample coagulation or platelet clumping is suspected, the CBC should be repeated. If the second blood draw confirms that the first draw yielded a falsely low platelet count, the result of the first draw should be ignored and the dose of bomedemstat calculated based on the result of the second draw.
5. Prophylactic platelet transfusion is at the discretion of the treating investigator. Prophylactic platelet transfusion is strongly encouraged for platelet count < 10x10³/mCL.

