6.0 TREATMENT PLAN

6.1 Study Overview

This is an open label, single arm, single institution Phase 1-2 study testing the activity and tolerability of the LSD1 inhibitor bomedemstat in combination with maintenance immune checkpoint inhibitor (ICI) in patients with newly diagnosed extensive stage SCLC treated with first-line induction platinum-etoposide and ICI. Bomedemstat dosing will be titrated to platelet count suppression (an on-target toxicity). Consideration of bomedemstat dose escalation will occur on an every three week schedule. As such, for convenience, all patients will receive the ICI atezolizumab in combination with bomedemstat, including patients who received a different ICI as part of induction with platinum-etoposide.

The starting dose of bomedemstat will be determined according to the screening platelet count as follows. For patients with a platelet count of $\geq 100 \times 10^3/\text{mCL}$, the starting dose will be 0.5 mg/kg/d. For patients with a platelet count of $75-99 \times 10^3/\text{mCL}$, the starting dose will be 0.4 mg/kg/d. See Sections 2.7 and 3.1.4 for bomedemstat starting dose selection rationale. A safety evaluation will be performed as described in Section 10.2 and the starting dose will be modified accordingly, if necessary.

Bomedemstat will be administered orally, once daily, for a 21-day cycle. Bomedemstat should be taken on an empty stomach. See Section 3.1.5 for detailed administration instructions. Because bomedemstat exhibits on-target toxicity of lineage-specific myelosuppression that preferentially affects platelet production, bomedemstat dosing will be titrated to a target platelet count of $50-99 \times 10^3/\text{mCL}$ as described in Section 6.2. Detailed guidance regarding bomedemstat dose modification for toxicities (including myelosuppression) is described in Section 6.3.

Atezolizumab will be administered via IV infusion at a flat dose of 1,200 mg every 3 weeks in keeping with the medication's prescribing information regarding standard of care use⁴⁶.

Subjects who at any time experience severe toxicity meeting criteria for treatment discontinuation (see Section 6.6.2) will not be eligible for further study treatment and will be converted to Off Treatment status.

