6.3 Dose Modification for Toxicity

Toxicity will be graded using Common Terminology Criteria for Adverse Events (CTCAE version 5.03). Dose modification of bomedemstat for hematologic toxicities is listed in Table 6.3. Please note that use of hematopoietic growth factors is prohibited during study participation (see Section 6.4.3). Dose modification of bomedemstat for other toxicities potentially related to bomedemstat is listed in Table 6.4. If multiple toxicities suggesting conflicting dose modifications are present simultaneously, the rule that results in the lowest bomedemstat dose should be followed.

Dose modification, interruption, or discontinuation of atezolizumab for toxicity should be performed according to the prescribing information⁴⁶.

Subjects that require more than three down-titrations or dose holds of bomedemstat will render the subject ineligible for further treatment in the study and the subject will be converted to Off Treatment status.

Furthermore, encephalopathy of any grade is always considered a serious adverse event as well as an unacceptable toxicity and should result in immediate treatment discontinuation (see Sections 8.6.1 and 10.2.1).

Table 6.3. Dose modification of bomedemstat related to hematologic toxicities.

Toxicity	Grade	Management ¹
Neutropenia	3 (ANC 0.5-1x10 ³ /mcL)	Continue bomedemstat dosing and maintain dose level.
	4 (ANC <0.5x10 ³ /mcL)	Hold bomedemstat dosing until ANC recovery to $\geq 1.0 \times 10^3$ /mcL. Reduce dose by 0.1 mg/kg/d upon reinitiating.
Febrile Neutropenia	≥ 3	Hold bomedemstat dosing for at least 7 days and until ANC recovery to $\geq 1.0 \times 10^3$ /mcL. Reduce dose by 0.1 mg/kg/d upon reinitiating.
Anemia	3 (Hgb <8 g/dL)	Continue bomedemstat dosing and maintain dose level. Transfusion of red blood cells is at the discretion of the treating physician and does not require bomedemstat dose modification.
	4 (Life-threatening consequences; urgent intervention indicated)	Hold bomedemstat dosing until Hgb recovery to ≥ 8 g/dL. Reduce dose by 0.1 mg/kg/d upon reinitiating.
Thrombocytopenia	See Table 6.1 and Table 6.2.	
Lymphopenia	Any	Dose interruption or study discontinuation is not required for lymphopenia of any grade.

1. Use of hematopoietic growth factors is prohibited during study participation (see Section 6.4.3).

Table 6.4. Dose modification of bomedemstat related to non-hematologic toxicities.

Type	Grade	Management			

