		Hold treatment?	Timing for restarting treatment	Dose/schedule for restarting/treatment	Discontinue subject? (After consultation with PI)
Non-laboratory	1	No	N/A	N/A	N/A
	2	Consider withholding for persistent symptoms	Toxicity resolves to Grade 0-1 or baseline	Reduce dose by 0.1 mg/kg/d upon reinitiating.	Toxicity does not resolve to Grade ≤ 1 or baseline

	3, lasting >3 days despite optimal supportive care	Yes			within 4 weeks of last dose. Permanent discontinuation should be considered for any severe or life-threatening event.
	4	Yes			
Laboratory, non-hematologic or hematologic not listed in Table 7-4	1-2	Consider withholding for clinically significant abnormalities following consultation with study PI	N/A	N/A	N/A
	3-4, if medical intervention is required or abnormality leads to hospitalization	Yes	Toxicity resolves to Grade 0-1 or baseline	Reduce dose by 0.1 mg/kg/d upon reinitiating.	Toxicity does not resolve to Grade ≤1 within 4 weeks of last dose. Permanent discontinuation should be considered for any severe or life-threatening event.

In case clinically significant non-hematologic toxicity does not resolve to Grade 0-1 or baseline within 4 weeks after last dose of any study treatment, investigational treatment with bomedemstat should be permanently discontinued, and the subject should be converted to Off Treatment status. Clinical significance is at the discretion of the investigator. With investigator and sponsor agreement, subjects with a non-hematologic laboratory adverse event still at Grade 2 after 4 weeks may continue treatment in the study and retain On Treatment status only if asymptomatic and controlled.

Subjects who experience a recurrence of the same severe or life-threatening event at the same grade or greater following re-challenge of bomedemstat are not eligible for further study treatment and should be converted to Off Treatment status.

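### After a 0.1 mg/kg/d toxicity reduction, the first Table 6.2 increase can return the patient to the dose at which the toxicity occurred, or 0.05 mg/kg/d above it, and nothing in the protocol limits increases by reference to that dose

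*Combined protocol and SAP*

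**What the plan says.** **Reduction.** Table 6.3 (Grade 4 neutropenia, febrile neutropenia, Grade 4 anemia) and Table 6.4 (qualifying toxicities outside Table 6.3, mainly non-hematologic) give the same instruction for restarting after a hold: "Reduce dose by 0.1 mg/kg/d upon reinitiating".

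**Increase.** From Cycle 2 Day 1, titration follows Table 6.2. At platelets of 200 or more the instruction is "Increase current dose by 0.15 mg/kg". At 100-199 the step is 0.1 mg/kg, unless the count has fallen by 75% or more, in which case the dose is kept.

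**Conditions on an increase.** Section 6.2 states: "Dose increases require adequate neutrophil and erythrocyte indices, and dose increases are not permitted within 21 days of a previous dose change". Table 6.2 footnote 1 makes this specific: ANC of at least 1.0 x10³/mcL and Hgb of at least 8 g/dL "are needed for up-titration or re-challenge". The only dose ceiling is 6 mg/kg/d, the same for every patient.

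**Conflict and recurrence.** Where several toxicities are present at the same time and point to different modifications, Section 6.3 says "the rule that results in the lowest bomedemstat dose should be followed". It also takes off treatment "Subjects who experience a recurrence of the same severe or life-threatening event at the same grade or greater following re-challenge".

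**The concern.** A toxicity reduction should leave the patient at a lower dose until someone judges that the earlier dose can be tried again. Here the reduction (0.1) is no larger than the smallest upward step (0.1) and is smaller than the other (0.15), so one increase cancels it. What triggers the increase is a platelet count above target.

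For a Grade 3-4 non-hematologic event, none of the values that gate the increase (platelets, ANC, Hgb) shows whether the patient can tolerate the event dose again. Some of these events, and febrile neutropenia, are DLT items in Section 9.5 when they are treatment-related and occur in the first 21 days. At stake is re-exposure to the dose that produced such an event, as a table default rather than a recorded decision. If the same severe event recurs, the patient comes off treatment. That could also count toward the Section 10.2.2 rule, which stops the study at four permanent cessations for unacceptable toxicity.

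**Working it through.** **Inputs.** Restart after a toxicity hold: -0.1 mg/kg/d (Tables 6.3 and 6.4). Increase: +0.1 at platelets 100-199 or +0.15 at 200 or more (Table 6.2). Lockout after any dose change: 21 days. Cap: 6 mg/kg/d. Starting doses: 0.5 or 0.4 mg/kg/d, with dispensing rounded to the nearest 5 mg (Section 3.1.4). The plan gives no figure of its own to reproduce.

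**Formula.** For event dose d, the restart dose is d - 0.1. The first increase gives:

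- platelets 100-199: d - 0.1 + 0.1 = d
- platelets 200 or more: d - 0.1 + 0.15 = d + 0.05

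The relative excess in the second case is 0.05/d.

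| Event dose d | Restart | After +0.1 | After +0.15 | Excess of the +0.15 path |
|---|---|---|---|---|
| 0.4 | 0.3 | 0.4 | 0.45 | 12.5% |
| 0.5 | 0.4 | 0.5 | 0.55 | 10% |
| 0.65 | 0.55 | 0.65 | 0.70 | 7.7% |
| 1.0 | 0.9 | 1.0 | 1.05 | 5% |
| 2.0 | 1.9 | 2.0 | 2.05 | 2.5% |
| 6.0 (cap) | 5.9 | 6.0 | 6.0 (capped) | none |

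**Dispensed doses.** At 70 kg with d = 0.5 the sequence is 35 mg, 30 mg, then 35 mg (+0.1) or 40 mg (+0.15: 0.55 x 70 = 38.5, rounded to 40). At 70 kg with d = 0.4, rounding hides the excess: 0.45 x 70 = 31.5, dispensed as 30 mg, the same as the event dose.

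Over whole-kg weights 45-110 (an assumed range of 66 weights, ties rounded up), the +0.15 path compares with the event dose as follows:

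| d | More dispensed | Same | Less |
|---|---|---|---|
| 0.4 | 49 | 17 | 0 |
| 0.5 | 46 | 20 | 0 |
| 0.65, 1.0, 2.0 (each) | 51 | 15 | 0 |

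**When the path does not arise.** Suppose a Table 6.2 down-titration intervenes after a restart at 0.4. The new dose is the lower of 0.4 - 0.1 = 0.3 and 0.75 x 0.4 = 0.3. The next increase gives 0.4 or 0.45, both below the event dose of 0.5. Also outside the path are Grade 3 neutropenia and Grade 3 anemia (no reduction), platelets below 50 (restart at half dose) and encephalopathy (off treatment).

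**Search for a limit.** Each provision that might close the path was set against it:

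- *ANC and Hgb gate.* For Grade 4 neutropenia, febrile neutropenia and Grade 4 anemia it checks the affected lineage. Its thresholds (1.0 and 8) equal the Table 6.3 recovery thresholds and are read at the reduced dose. They show that the patient has recovered and is holding at d - 0.1, not that d is tolerable.
- *Lowest-dose rule.* It covers concurrent toxicities; a resolved one is no longer present.
- *Section 3.1.6.* The PI guides re-start after an SAE-related hiatus. Later increases are not mentioned.
- *Section 3.1.4.* The PI is consulted on uncertainty, but the Table 6.2 cells read as settled instructions.
- *Table 6.4 and Section 6.6.2.* Permanent discontinuation is to be considered after severe events, and the investigator may stop treatment. Neither sets a rule for a patient who continues.
- *Section 6.2.* Safety reductions are allowed at any time. This permits a lower dose but does not bar a higher one.
- *Removal on recurrence, and after more than three down-titrations or holds.* Both act after a further event.
- *Sections 8.3.1 and 12.0.* Laboratory results must be acceptable before each cycle, and data are reviewed weekly. Neither states a re-escalation rule.

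None refers to the event dose.

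**The case against.** The strongest reply is that re-titration is the design. Section 3.1.4 expects the required dose to differ between patients and over time, and Section 6.1 leaves room for judgment: "Consideration of bomedemstat dose escalation will occur on an every three week schedule". An early cytopenia may reflect recent induction chemotherapy, so a fixed lifetime ceiling could be wrong. The excess is 0.05 mg/kg/d at most, and 0.55 is still below the 0.6 mg/kg/d starting dose used in the other Phase 2 studies (different populations, Section 2.7). This is a single-institution trial with weekly review by the PI and staff, and the PI already guides re-start after SAEs. All of this stands. It argues against banning re-escalation and against a high severity. It does not supply the missing rule: Section 6.2 says titration should follow Table 6.2, whose cells are directive.

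A reader might infer three stronger claims:

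- *That the platelet count alone decides re-escalation.* Not supported: every increase also needs adequate ANC and Hgb and 21 days without a dose change.
- *That every such path follows a severe event.* Not supported: Table 6.4 applies the same reduction after an optional hold for persistent Grade 2 symptoms.
- *That Section 6.2 contradicts Tables 6.3 and 6.4 on the restart dose.* The sentence that after a hold "the subject should be re-challenged with bomedemstat at 50% of the previous dose" gives no reason for the hold. But it is conditioned on platelet recovery, and both titration tables place the 50% rule only in the row below 50. The point is editorial.

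**Conclusion.** The gap is real but modest and conditional. It requires recovery and restart after a 0.1 mg/kg/d reduction, Cycle 2 or later, at least 21 days since the last dose change, adequate ANC and Hgb, platelets of at least 100, no intervening reduction, and a dose below the cap. Under those conditions Table 6.2 as written directs a return to the event dose, or 0.05 mg/kg/d above it at platelets of 200 or more. The case is strongest for Grade 3-4 events under Table 6.4 and weaker for Table 6.3 events, where the gate at least checks the affected lineage.

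The dispensing counts rest on an assumed weight range. The documents give no frequency for the path, so no expected number of patients can be stated. They also do not show that patients would be re-exposed without supervision: the existing safeguards lower that risk but set no re-escalation rule. The change is worth making because it is cheap and addresses safety; the design is not invalid without it.

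**What to change.** Add to Section 6.2, and as a footnote on both up-titration rows of Table 6.2:

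*After a reduction under Table 6.3, or under Table 6.4 for a Grade 3-4 event, no platelet-driven increase may reach or exceed the dose at which the toxicity occurred unless the PI gives documented approval.*

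Limiting the Table 6.4 part to Grade 3-4 keeps optional Grade 2 holds out of the requirement. Re-escalation remains possible.

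**Cost.** One sentence and one footnote by amendment, with no extra visits or tests; approval can be given at the weekly review. Because the smallest step equals the reduction, the first increase after a single such reduction will always need sign-off, and some patients may stay above the 50-99 platelet target for longer.

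Optionally, state in Section 6.2 that the half-dose re-challenge applies to holds for platelets below 50 x10³/mcL.

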6.3 Dose Modification for Toxicity

Toxicity will be graded using Common Terminology Criteria for Adverse Events (CTCAE version 5.03). Dose modification of bomedemstat for hematologic toxicities is listed in Table 6.3. Please note that use of hematopoietic growth factors is prohibited during study participation (see Section 6.4.3). Dose modification of bomedemstat for other toxicities potentially related to bomedemstat is listed in Table 6.4. If multiple toxicities suggesting conflicting dose modifications are present simultaneously, the rule that results in the lowest bomedemstat dose should be followed.

Dose modification, interruption, or discontinuation of atezolizumab for toxicity should be performed according to the prescribing information⁴⁶.

Subjects that require more than three down-titrations or dose holds of bomedemstat will render the subject ineligible for further treatment in the study and the subject will be converted to Off Treatment status.

Furthermore, encephalopathy of any grade is always considered a serious adverse event as well as an unacceptable toxicity and should result in immediate treatment discontinuation (see Sections 8.6.1 and 10.2.1).

Table 6.3. Dose modification of bomedemstat related to hematologic toxicities.

Toxicity	Grade	Management ¹
Neutropenia	3 (ANC 0.5-1x10 ³ /mcL)	Continue bomedemstat dosing and maintain dose level.
	4 (ANC <0.5x10 ³ /mcL)	Hold bomedemstat dosing until ANC recovery to $\geq 1.0 \times 10^3$ /mcL. Reduce dose by 0.1 mg/kg/d upon reinitiating.
Febrile Neutropenia	≥ 3	Hold bomedemstat dosing for at least 7 days and until ANC recovery to $\geq 1.0 \times 10^3$ /mcL. Reduce dose by 0.1 mg/kg/d upon reinitiating.
Anemia	3 (Hgb <8 g/dL)	Continue bomedemstat dosing and maintain dose level. Transfusion of red blood cells is at the discretion of the treating physician and does not require bomedemstat dose modification.
	4 (Life-threatening consequences; urgent intervention indicated)	Hold bomedemstat dosing until Hgb recovery to ≥ 8 g/dL. Reduce dose by 0.1 mg/kg/d upon reinitiating.
Thrombocytopenia	See Table 6.1 and Table 6.2.	
Lymphopenia	Any	Dose interruption or study discontinuation is not required for lymphopenia of any grade.

1. Use of hematopoietic growth factors is prohibited during study participation (see Section 6.4.3).

Table 6.4. Dose modification of bomedemstat related to non-hematologic toxicities.

Type	Grade	Management			
		Hold treatment?	Timing for restarting treatment	Dose/schedule for restarting/treatment	Discontinue subject? (After consultation with PI)
Non-laboratory	1	No	N/A	N/A	N/A
	2	Consider withholding for persistent symptoms	Toxicity resolves to Grade 0-1 or baseline	Reduce dose by 0.1 mg/kg/d upon reinitiating.	Toxicity does not resolve to Grade ≤ 1 or baseline

	3, lasting >3 days despite optimal supportive care	Yes			within 4 weeks of last dose. Permanent discontinuation should be considered for any severe or life-threatening event.
	4	Yes			
Laboratory, non-hematologic or hematologic not listed in Table 7-4	1-2	Consider withholding for clinically significant abnormalities following consultation with study PI	N/A	N/A	N/A
	3-4, if medical intervention is required or abnormality leads to hospitalization	Yes	Toxicity resolves to Grade 0-1 or baseline	Reduce dose by 0.1 mg/kg/d upon reinitiating.	Toxicity does not resolve to Grade ≤1 within 4 weeks of last dose. Permanent discontinuation should be considered for any severe or life-threatening event.

In case clinically significant non-hematologic toxicity does not resolve to Grade 0-1 or baseline within 4 weeks after last dose of any study treatment, investigational treatment with bomedemstat should be permanently discontinued, and the subject should be converted to Off Treatment status. Clinical significance is at the discretion of the investigator. With investigator and sponsor agreement, subjects with a non-hematologic laboratory adverse event still at Grade 2 after 4 weeks may continue treatment in the study and retain On Treatment status only if asymptomatic and controlled.

Subjects who experience a recurrence of the same severe or life-threatening event at the same grade or greater following re-challenge of bomedemstat are not eligible for further study treatment and should be converted to Off Treatment status.

